3.3.2 Exclusion Criteria

1. Target Disease Exceptions

- a) Presence of Type 1 diabetes, as demonstrated by:
 - Preexisting diagnosis of Type 1 diabetes,

OR

- Positivity at screening of either antibodies to glutamic acid decarboxylase (GAD) or
 protein tyrosine phosphatase-like protein antibodies (IA-2) AND abnormally low
 levels of C-peptide. GAD and IA-2 antibody testing will be performed in all screened
 subjects, C-peptide only in otherwise eligible, antibody-positive subjects. All instances
 of antibody-positive subjects with normal or elevated C-peptide values will be
 discussed by the Investigator with the study medical monitors and Sponsor's study
 director to confirm study eligibility. 14,15,16
- b) Previous diagnosis of monogenic etiology of Type 2 diabetes such as maturity onset diabetes of the young (MODY), genetic disorders with strong associations with insulin resistance/diabetes and/or obesity such as Turner's Syndrome and Prader-Willi, or secondary diabetes (steroid use, Cushing's disease, acromegaly), secondary diabetes mellitus, or diabetes insipidus
- c) Diabetes ketoacidosis within 6 months of screening
- d) Current use of the following medications for the treatment of diabetes, or use within the specified timeframe prior to screening for the main study:
 - i) Eight weeks: sulfonylureas, alpha glucosidase inhibitors, metiglinide, oral or injectable incretins or incretin mimetics, other anti-diabetes medications not otherwise specified.

- ii) Sixteen weeks: thiazolidinediones, DPP-4 inhibitors (with no reported medication related AEs related to DPP-4 inhibitors), SGLT-2 inhibitors (with no reported medication related AEs related to SGLT-2 inhibitors)
- e) Initiation or discontinuation of prescription or non-prescription weight loss drugs within 8 weeks of screening. Use of prescription or non-prescription weight loss drugs must be stable during the study.

2. Medical History and Concurrent Diseases

- a) Pregnant, positive serum pregnancy test, planning to become pregnant during the clinical trials, or breastfeeding
- b) History of unstable or rapidly progressive renal disease
- c) History of unresolved vesico-ureteral reflux
- d) History of or current, acute or chronic pancreatitis
- e) History of hemoglobinopathy, with the exception of sickle cell trait or thalassemia minor; or chronic or recurrent hemolysis
- f) Malignancy within 5 years of the screening visit (with the exception of treated basal cell or treated squamous cell carcinoma)
- g) Significant co-morbidity that, in the opinion of the Investigators, will increase the risk to the subject such as immunosuppression, or current treatment for cancer
- h) Replacement or chronic systemic corticosteroid therapy, defined as any dose of systemic corticosteroid taken for > 4 weeks within 3 months prior to the Day 1 visit

NOTE: inhaled, nasal spray, or topical steroids if limited to minor surface area are allowed.

3. Physical and Laboratory Test Findings

- a) Abnormal renal function, which is defined as an estimated glomerular filtration rate (eGFR) calculated by the Schwartz Formula $< 80 \text{ mL/min/1.73 m}^2 (1.33 \text{ mL/s})^{17}$
- b) An abnormal thyroid-stimulating hormone (TSH) value at enrollment will be further evaluated for free T4. Subjects with abnormal free T4 values will be excluded.

(Note: In subjects who have had a prior diagnosis of a thyroid disorder and who are currently receiving thyroid replacement therapy, retest of TSH may be allowed, as determined by the Investigator, after a minimum of 6 weeks following the adjustment of thyroid hormone replacement therapy. Such cases should be discussed with the Sponsor prior to retesting. The subject must have all enrollment procedures and laboratory assessments performed as part of this retest, and all of these must meet enrollment eligibility criteria. The subject's number will however remain the same as initially assigned.)

c) Hematuria (confirmed by microscopy at screening) with no explanation as judged by the Investigator up to randomization.

- d) Aspartate aminotransferase (AST) or alanine aminotransferase (ALT) > 2× upper limit of normal (ULN), or clinically significant hepatic disease.
- e) Serum total bilirubin (TB) \geq 2x ULN unless exclusively caused by Gilbert's syndrome
- f) Positive serologic evidence of current infectious liver disease including anti-hepatitis A virus (HAV) (IgM), hepatitis B surface antigen (HBsAg), or anti-hepatitis C virus (HCV). Subjects who have isolated positive anti-hepatitis B surface antibodies may be included.
- g) Anemia of any etiology defined as hemoglobin ≤ 10.7 g/dL (107 g/L) for females and ≤ 11.3 g/dL (113 g/L) for males. Subjects who are considered to have anemia according to local guidelines should be excluded.
- h) Volume-depleted subjects. Subjects at risk for volume depletion due to co-existing conditions or concomitant medications, such as loop diuretics, should carefully monitor their volume status.
- Clinically significant abnormalities in any pre-Day 1 Randomization laboratory analyses or electrocardiogram (ECG) that, in the Investigator's opinion, would preclude randomization.

4. Allergies and Adverse Drug Reaction

a) Known allergy, sensitivity or contraindication to any study drug or its excipient/vehicle

5. Other Exclusion Criteria

- a) Subject is currently abusing alcohol or other drugs or has done so within the last 6 months prior to the screening visit.
- b) Prisoners or subjects who are involuntarily incarcerated. (Note: under certain specific circumstances a person who has been imprisoned may be included or permitted to continue as a subject. Strict conditions apply and Sponsor/designee approval is required.)
- c) Subjects who are compulsorily detained for treatment of either a psychiatric or physical (e.g., infectious disease) illness.
- d) Psychiatric or cognitive disorder that will, in the opinion of investigators, limit the subject's ability to comply with the study medications and monitoring.
- e) Subjects who have contraindications to therapy as outlined in the saxagliptin and dapagliflozin Investigator Brochure or local package inserts.
- f) Participation and receiving IP in another clinical study during the prior 3 months.

Eligibility criteria for this study have been carefully considered to ensure the safety of the study subjects and that the results of the study can be used. It is imperative that subjects fully meet all eligibility criteria.

3.3.3 Women of Childbearing Potential

A WOCBP is defined as any female who has experienced menarche and who has not undergone surgical sterilization (hysterectomy or bilateral oophorectomy) and is not postmenopausal.

3.4 Screen Failures

Screen failures are defined as subjects who signed the informed consent form to participate in the clinical study but are not subsequently randomly assigned to study treatment. A minimal set of screen failure information is required to ensure transparent reporting of screen failure subjects to meet the Consolidated Standards of Reporting Trials publishing requirements and to respond to queries from Regulatory Authorities. Minimal information includes demography, screen failure details, eligibility criteria, and any SAE.

Individuals who do not meet the criteria for participation in this study (screen failure) may be re-screened twice. A re-screened subject will be assigned a new subject number that is different from that assigned during the initial screening. Re-screening should be documented so that its effect on study results, if any, can be assessed.

These subjects should have the reason for study withdrawal recorded in the electronic case report form (eCRF).

3.5 Concomitant Treatments

3.5.1 Prohibited and/or Restricted Treatments

- Once consented subjects may not receive any prescription antihyperglycemic medication other than study drug, metformin and/or insulin.
- Once consented, subjects should not begin treatment with any systemic corticosteroid therapy lasting ≥ 5 days of therapy (inhaled, nasal, and topical are allowed). Subjects who require systemic corticosteroid therapy should be discussed with the Medical Monitor prior to starting therapy whenever possible.
- Once consented, subjects should not commence or modify therapy with any prescription or over-the-counter weight loss medications.
- Once consented, subjects should not undergo any bariatric surgery.
- Once consented, subjects should not commence therapy with potent cytochrome P450 3A4/3A5 (CYP3A4/5) inhibitors in countries where dose adjustment due to potent systemic CYP3A4/5 inhibitor use would be required by the saxagliptin label.

3.5.2 Other Restrictions and Precautions

- Subjects must comply with their prescribed dosing regimen to preserve study integrity and ensure subject safety.
- Subjects should be cautioned that any new prescription, over-the-counter or herbal/nutritional
 therapies should be discussed thoroughly with the Investigator as concomitant use could result

in alterations to their glycemic control and may place them at risk for significant hypoglycemic episodes.

- Medication other than those which are protocol prohibited as described above, considered
 necessary for the subject's safety and wellbeing, may be given at the discretion of the
 Investigator and must be recorded in the appropriate sections of the case report form (CRF).
- Subjects must make every attempt to adhere to the diet and exercise counseling and to the study flow chart/time and events schedule (see Section 5.1).
- Women of childbearing potential must immediately contact the Investigator if they suspect
 they might be pregnant and if they have changed or plan to change their birth control method.

3.6 Discontinuation of the Study

The Sponsor designee reserves the right to close the study site or terminate the study at any time for any reason at the sole discretion of the Sponsor. Study sites will be closed upon study completion. A study site is considered closed when all required documents and study supplies have been collected and a study-site closure visit has been performed.

The investigator may initiate study-site closure at any time, provided there is reasonable cause and sufficient notice is given in advance of the intended termination.

Reasons for the early closure of a study site by the Sponsor or Investigator may include but are not limited to:

- Failure of the investigator to comply with the protocol, the requirements of the IRB/IEC or local Health Authorities, the Sponsor's procedures, or GCP guidelines
- Inadequate recruitment of participants by the investigator
- Discontinuation of further study intervention development

If the study is prematurely terminated or suspended, the Sponsor shall promptly inform the investigators, the IECs/IRBs, the Regulatory Authorities, and any contract research organization(s) used in the study of the reason for termination or suspension, as specified by the applicable regulatory requirements. The Investigator shall promptly inform the participant and should assure appropriate participant therapy and/or follow-up.

3.7 Discontinuation of Investigational Product Following Any Treatment with Study Drug

Subjects MUST discontinue IP (and non-IP at the discretion of the Investigator) for any of the following reasons:

- Subject's request to stop study treatment
- Any clinical AE, laboratory abnormality or intercurrent illness which, in the opinion of the Investigator, indicates that continued participation in the study is not in the best interest of the subject
- Termination of the study by the Sponsor/designee

- Loss of ability to freely provide consent through imprisonment or involuntary incarceration for treatment of either a psychiatric or physical (e.g., infectious disease) illness
- Unblinding a subject for any reason (emergency or non-emergency)
- Severe non-compliance to protocol, as judged by the Investigator and/or Sponsor/designee
- Safety reasons as judged by the Investigator and/or Sponsor/designee
- Pregnancy
- For subjects on metformin, development of contraindications to metformin therapy as per local label
- Subjects experiencing decreased renal function must be evaluated as per Investigator's discretion
 - ◆ Subjects with eGFR < 50 mL/min for sustained period of time (12 to 16 weeks) must be discontinued
- Subjects with a central laboratory ALT and/or AST > 3xULN will be scheduled for a follow-up visit within 3 days following the receipt of the result (see Appendix 1 and Appendix 2 for further guidance). Subjects should be discontinued from study drug if the initial and repeat laboratory tests meet any of the following criteria:
 - ◆ ALT and/or AST are > 3x ULN and TB > 2x ULN
 - ◆ ALT and/or AST are > 5x ULN for ≥ 14 consecutive days, at any time after initial confirmatory results
 - ALT and/or AST are ≥ 10x ULN

In the case of pregnancy, the Investigator must immediately notify the Sponsor Medical Monitor/designee of this event. The study drug will be permanently discontinued in an appropriate manner.

All subjects who discontinue IP early (prior to the Week 52 visit) will remain in the study and should comply with protocol-specified follow-up procedures including site visits and phone contacts as outlined in Section 5. The only exception to this requirement is when a subject withdraws consent for all study procedures including post-treatment study follow-up or loses the ability to consent freely (i.e., is imprisoned or involuntarily incarcerated for the treatment of either a psychiatric or physical illness).

If a subject discontinues IP early (prior to the Week 52 visit), at the next visit the subject should be assessed according to the follow-up schedule for Early Treatment Discontinuation (ETD) (Table 5.1-4). The reason for early discontinuation must be documented in the subject's medical records and entered on the appropriate CRF page.

Subjects who discontinue IP early will still be evaluated for rescue.

After discontinuation of IP the management of the subject's diabetes will be under the care and direction of the Investigator.

3.7.1 Procedures for Handling Patients Incorrectly Enrolled or Randomized

Subjects who fail to meet the inclusion/exclusion criteria must not, under any circumstances, be enrolled or randomized. There can be no exceptions to this rule.

Subjects who are incorrectly enrolled, but are not yet randomized, should be withdrawn from the study. The procedures included in the protocol for the discontinuation of such subjects must be followed. Subjects should be further treated according to the Investigator's judgment and local therapy tradition.

If a subject not meeting the study criteria is randomized in error, and if the error is identified after Day 1 Randomization, a discussion must occur between the Sponsor Medical Monitor/designee and the Investigator regarding whether to continue or discontinue the subject from the study drug. If agreement to continue in the study is reached, the subject should complete the study unless there are safety concerns or if the subject withdraws the consent. In situations in which an agreement cannot be reached, the subject should have the randomized therapy stopped and be discontinued from the study. The procedures included in the protocol for the discontinuation of such subjects must be followed. The Sponsor Medical Monitor/designee is to ensure all such contacts with the Investigator and such decisions are appropriately documented.

Withdrawn subjects will not be replaced.

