3.8 Post-Study Drug Follow-up

Post-study drug follow-up is of critical importance and is essential to preserving subject safety and the integrity of the study. Subjects who discontinue study drug must continue to be followed for collection of outcome and/or survival follow-up data as required and in line with Section 5 until death or the conclusion of the study.

Please note that after the discontinuation of study drug, the management of the subject's diabetes will be under the care and direction of the Investigator.

The only exception to any of these follow-up methods are when a subject withdraws consent for all study procedures, including post-treatment study follow-up or loses the ability to consent freely (i.e., is imprisoned or involuntarily incarcerated for the treatment of either a psychiatric or physical illness).

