3.8.1 Withdrawal of Consent

Subjects who request to discontinue study drug will remain in the study and must continue to be followed for protocol-specified follow-up procedures. The only exception to this is when a subject specifically withdraws consent for any further contact with him/her or persons previously authorized by subject to provide this information. A subject who considers withdrawing from the study must be informed by the investigator about modified follow-up options (e.g., site visits with limited procedures, home nursing, phone calls, less frequent visits, or continuation in the study without further treatment).

Subjects should notify the Investigator of the decision to withdraw consent from future follow-up **in writing**, whenever possible. A subject who withdraws consent will always be asked about the reason(s) and the presence of any AE. The withdrawal of consent should be explained in detail in the medical records by the Investigator, as to whether the withdrawal is from further treatment with study drug only or also from study procedures and/or post-treatment study follow-up, and

entered on the appropriate CRF page. If deemed necessary, the Investigator will follow-up subjects as medically indicated.

If a subject withdraws consent for disclosure of future information, the Sponsor may retain and continue to use any data collected before such a withdrawal of consent. If a subject withdraws from the study, it should be confirmed if he/she still agrees for existing samples to be used in line with the original consent. If he/she requests withdrawal of consent for use of samples, destruction of any samples taken and not tested should be carried out in line with what was stated in the informed consent and local regulation The investigator must document the decision on use of existing samples in the site study records and inform the Global Study Team.

Withdrawal of Informed Consent for donated biological samples

If a subject withdraws consent to the use of donated biological samples, the samples will be destroyed, and the action documented. If samples are already analyzed, the Sponsor is not obliged to destroy the results of this research.

The investigator must ensure:

- Subject's withdrawal of informed consent to the use of donated samples is notified immediately to the Sponsor/designee.
- Biological samples from that subject, if stored at the study site, are immediately identified, destroyed, and the action documented.

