5.3.10.2 Early Treatment Discontinuation Visit

Any subject who discontinues during the study periods must have all ETD visit procedures performed before study discontinuation. The IXRS must be called to record the subject status (i.e., ETD status). All subjects who discontinue study drug should remain in the study.

After ETD visit procedures are performed, the subject will continue in the treatment period according to the Early Discontinued follow-up visit schedule (Table 5.1-4).

The ETD supplemental eCRF will need to be completed.

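### Protocol Section 3.7.1 takes some wrongly randomized subjects out of the study, against the rule in Sections 3.7, 3.8 and 5.3.10.2 that everyone who stops study drug stays in follow-up

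*Protocol*

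**What the plan says.** Protocol Section 3.7.1 deals with subjects found after Day 1 randomization not to meet the criteria. The medical monitor and the investigator must hold a discussion "regarding whether to continue or discontinue the subject from the study drug". If they agree that the subject continues, the subject should complete the study, barring safety concerns or withdrawn consent. If they cannot agree, "the subject should have the randomized therapy stopped and be discontinued from the study". The section then adds: "The procedures included in the protocol for the discontinuation of such subjects must be followed".

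The parent section, 3.7, sets the general rule: "All subjects who discontinue IP early (prior to the Week 52 visit) will remain in the study". It limits the exceptions: "The only exception to this requirement is when a subject withdraws consent for all study procedures", or when the ability to consent freely is lost. The rule is repeated three times:

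- Section 3.8: "Subjects who discontinue study drug must continue to be followed for collection of outcome and/or survival follow-up data", with the same exceptions.
- Section 3.8.1: "Subjects who request to discontinue study drug will remain in the study and must continue to be followed".
- Section 5.3.10.2: "All subjects who discontinue study drug should remain in the study".

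None of these places makes an exception for wrongly randomized subjects.

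**The concern.** A subject who has been dosed and then stops drug under Section 3.7.1 is also a subject who stops drug early under Section 3.7. One section ends participation and the other requires it to go on. A failure to agree is not among the exceptions that Section 3.7 describes as the only ones.

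The contradiction touches the analysis because the trial relies on data collected after drug is stopped. The primary estimand uses HbA1c regardless of premature treatment discontinuation (Protocol 8.4.2.1, SAP 4.4.1), and the primary efficacy set keeps every randomized subject who took at least one dose (Protocol 8.2, SAP 2.2.2). A site that follows Section 3.7.1 literally therefore creates a missing value by instruction, in a subject whom the analysis still counts. It also ends scheduled observation of a child who has been exposed to study drug.

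**Working it through.** **Step 1. Can the two instructions be reconciled?** Section 3.7.1 gives two actions joined by *and*: stop therapy, and leave the study. Section 3.7 covers the first and forbids the second outside its named exceptions. The sentence in 3.7.1 on following discontinuation procedures comes after the explicit instruction to leave, so it does not cancel it. For a dosed subject the conflict stands. A subject randomized but never dosed is outside the primary efficacy set, and outside Section 3.7, whose heading limits it to the time after any treatment with study drug. For that subject the primary analysis is not affected.

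**Step 2. What is lost when a dosed subject exits?**

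- *Week 26 HbA1c.* The early-discontinuation visit draws HbA1c (Protocol Table 5.1-2, Section 5.3.10.2), but SAP Table 9 assigns a sample to Week 26 only from day 163. Without a sample in that window the value is imputed.
- *Retrieved drop-out status.* SAP 4.1.12 requires that the subject left treatment but not the study, so this subject cannot qualify. The preferred imputation method needs at least 5 such observations in each imputation model.
- *Scheduled follow-up in Table 5.1-4.* This means HbA1c and FPG visits, adverse event contacts (quarterly after Week 56), and the Week 104 growth and maturity assessments. It is not a complete loss of safety data: Section 6.1.1 still collects serious events within 28 days of the last dose, and Sections 6.1.1 and 6.2.1 still require known events to be followed.

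**Step 3. Reproduce the plan's power.** Inputs from Protocol 8.1 and 3.1: difference 0.75, SD 1.7, two-sided alpha 0.05, 81 per arm.

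- SE = 1.7 × √(1/81 + 1/81) = 0.2671
- Power: normal approximation 80.2%, noncentral t 79.7%. Both agree with the stated figure of approximately 80%.

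**Step 4. Effect of one exit on power.** Take the extreme case in which all of one subject's information in one arm is lost.

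- SE = 1.7 × √(1/80 + 1/81) = 0.2680
- Power (noncentral t): 79.4%, a drop of about 0.3 percentage points

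**Step 5. Effect of one exit on the estimate.** The documents give no figure for the gap between the imputed value and the value that would have been observed. Assume 0.5 to 1.0 HbA1c points.

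- Shift in the arm mean: 0.5/81 = 0.006 to 1.0/81 = 0.012 points
- In standard errors: 0.006/0.2671 = 0.02 to 0.012/0.2671 = 0.05

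**Step 6. Follow-up time lost by one exit before day 163.** Week 104 has target day 728 (SAP Table 10), and the visit may be up to 28 days early (Protocol Table 5.1-4).

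- To the earliest permitted visit: 728 − 28 = 700, and 700 − 163 = 537, so more than 537 days (about 77 weeks)
- To the target day: 728 − 163 = 565, so more than 565 days (about 81 weeks)

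**The case against.** The best defence has four parts.

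1. *A specific rule may override a general one.* Section 3.7.1 concerns minors who should not have been randomized, and sparing them further visits and blood draws is a defensible aim. But Section 3.7 calls its exceptions the only ones, and 3.7.1 does not say that it departs from them. If the carve-out is meant, it needs to be written.
2. *The procedures sentence may lead back to follow-up.* For a dosed subject, the discontinuation procedures are those in Sections 3.7 and 5.3.10.2, which end in Table 5.1-4. This is a possible reading of the intent. It does not remove the explicit instruction to leave the study that stands just before it.
3. *The protocol uses study discontinuation loosely elsewhere.* Section 5.3.10.2 and the liver panel text in Appendix 1 do so. That is true, and it suggests that the text in 3.7.1 may be a slip. The slip matters more there, because stopping therapy and leaving the study are listed as two separate actions.
4. *The effect is close to nil.* An eligibility error, a dosed subject and a failure to agree must all coincide. The SAP reports both imputation methods (4.4.1) and a tipping-point analysis (4.4.2.4). This stands in full.

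A reader might also infer that disagreement ends follow-up while a joint decision to stop drug preserves it. The text does not support that firmly. Section 3.7.1 moves from continuing study drug to continuing in the study without separating the two, so failing to agree may simply mean that no agreement to continue was reached. That would include a joint decision to stop.

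A reader might likewise see a second exit route in the severe hypoglycemia bullet of Section 3.7.3. That bullet is permissive, it sits under a list about stopping blinded drug, and the paragraph after it keeps drug discontinuers in follow-up. It and the wording in 5.3.10.2 and Appendix 1 are editorial matters, not part of this point.

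**Conclusion.** The contradiction is real and in the current protocol text. Section 3.7.1 ends participation for a dosed subject whom Sections 3.7, 3.8 and 5.3.10.2 keep in follow-up. It is a minor point. Per exit, the cost is at most about 0.3 percentage points of power. Under the assumed gap of 0.5 to 1.0 points, the estimated difference shifts by 0.02 to 0.05 standard errors. For the individual, an exit before day 163 loses more than 537 days of scheduled follow-up.

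The documents give no rate of randomization errors, failures to agree or exits, so no total effect can be calculated; it is probably very small. Nothing here supports a claim that the primary conclusion is at risk. Confidence is high that the texts conflict; the size rests on the assumptions stated.

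The analysis does not need the exit. SAP Table 2 already excludes several eligibility errors from the Evaluable Subjects Data Set (rows 1, 2, 10 and 11), while the intent-to-treat set keeps those subjects.

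**What to change.** In the sentence of Section 3.7.1 that covers failure to agree, keep the instruction to stop randomized therapy. Replace the instruction to leave the study with wording such as: *and, if study drug has been received, be followed per Table 5.1-4 unless consent is withdrawn or the ability to consent is lost*. The decision on whether and when drug stops is not changed.

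Make the change in a protocol amendment. It alters who stays under follow-up, and Section 9.1.1 requires documented IRB/IEC approval before a change is implemented. No new schedule is needed, because Table 5.1-4 exists. The downside is a few follow-up visits and blood draws for an ineligible child. Section 3.7 already requires them, and the family can decline them by withdrawing consent.
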